1.2.1. Justification for Dose Selection for Study

The regimen to be evaluated will be a fixed dose of 5.6 mg/kg administered as a continuous IV infusion on Day 1 of each 21-day cycle.

Data from two studies have been considered for the selection of the 5.6 mg/kg dose. Study U31402-A-J101 included 1.6 mg/kg, 3.2 mg/kg, 6.4 mg/kg and 8.0 mg/kg Q3W in subjects with breast cancer, the MTD was established at 6.4 mg/kg. Study U31402-A-U102 included 3.2-mg/kg, 4.8 mg/kg, 5.6 mg/kg and 6.4 mg/kg Q3W in NSCLC patients, the MTD was established at 5.6 mg/kg. In addition, 4.2 mg/kg every 2 weeks and an up-titration dose regimen were studied in the J101 study, with 3.2 mg/kg in Cycle 1, 4.8 mg/kg in Cycle 2, and 6.4 mg/kg in Cycle 3 and after. Exposure of intact U3-1402 ADC, total anti-HER3 Ab and released payload MAAA-1181a increased as dose increased. Population pharmacokinetics (PK), and exposure response analyses for efficacy and safety were conducted using data from both the U31402-A-J101 and U31402-A-U102 studies. Exposure-efficacy relationship was established for intact U3-1402 ADC and the exposure safety relationship was established for released payload MAAA-1181a.

The rationale for the selection of 5.6 mg/kg is based on an exposure-response analysis of efficacy, and 5.6 mg/kg is predicted to provide a lower probability of \geq Grade 3 thrombocytopenia compared to 6.4 mg/kg, and an improved ORR compared to 4.8 mg/kg.

More data are being collected in the ongoing U3-1402 studies to further evaluate this dosing regimen.

1.2.2. Benefit/Risk Assessment for Study Subjects

U3-1402 is being developed for the treatment of HER3-expressing malignant tumors.

Nonclinical studies have demonstrated the antitumor activity of U3-1402 in HER3 tumor-bearing mouse models. Thus, U3-1402 is hypothesized to demonstrate efficacy in treating HER3-expressing tumors in patients.

In nonclinical toxicology studies, intestinal toxicity, lymphatic/hematopoietic system toxicity, skin toxicity, pulmonary toxicity, reproductive and accessory organ toxicities, hepatic toxicity, cardiotoxicity, and renal toxicity were found in association with the administration of U3-1402.

As with any therapeutic Abs, there is a possibility of infusion-related reactions and immune responses causing allergic or anaphylactic reactions to U3-1402. Considering the toxicity data from the nonclinical studies, the important potential risk is hepatotoxicity, and the potential risks are infusion-related reaction, dry eye, keratitis, photosensitivity, dry skin, rash, rash maculopapular, and skin pigmentation in humans from exposure to U3-1402, and these have been closely monitored and evaluated in the U3-1402 clinical development program.

Based on the preliminary clinical safety data from the ongoing U3-1402 studies, the important identified risk is interstitial lung disease (ILD); the important potential risk is hepatotoxicity, and the identified risks are nausea, decreased appetite, platelet count decreased/thrombocytopenia, white blood cell count decreased/leukopenia, neutrophil count decreased/neutropenia, vomiting, anemia, diarrhea, fatigue, malaise, stomatitis, constipation, alanine aminotransferase (ALT) increased, AST increased, febrile neutropenia, and alopecia, and will continue to be closely monitored and evaluated in the U3-1402 clinical development program.

Preliminary data as of 06 Nov 2018 from the ongoing study U31402-A-J101 in breast cancer subjects from Dose Escalation and Dose Finding (N=42) demonstrated a confirmed ORR of 42.9%, a DCR of 90.5%, and a median PFS of 8.3 months (median follow-up of 10.5 months).²⁸ Further, preliminary data as of May 2019 from the ongoing study U31402-A-U102 are as follows: of the 26 efficacy-evaluable patients, 6 had confirmed PRs (2 each at 4.8, 5.6, and 6.4 mg/kg). Median best percentage change in SoD was -25.7% (range, -82.6% to 13.3%), including decreases in SoD in patients with CDK4 amplification (-25.7% and -17.8%), HER2 amplification (-28.6%), and both CCNE1 amplification and PIK3CA mutation (-28.8%).²⁹

In conclusion, based on the efficacy and safety data from the nonclinical studies and the preliminary clinical safety and efficacy data from the ongoing studies, the benefit/risk balance supports continued clinical development of U3-1402.

See the current IB for updated benefit/risk assessment.²⁶

2. STUDY OBJECTIVES, OUTCOME MEASURES, AND ENDPOINTS

The objectives and endpoints as well as outcome measures are described in [Table 2.1](#). See [Section 11](#) for further description of the endpoint analyses and definitions.

Table 2.1: Description of Objectives, Outcome Measures, and Endpoints

| Objectives | Outcome Measures | Endpoints | Category |
|--|--|--|----------|
| Primary | | | |
| To assess the antitumor activity of U3-1402 in subjects with advanced or metastatic CRC who are resistant, refractory, or intolerant to at least 2 prior lines of therapy (see Inclusion Criteria in Section 4.1) | 
Title: ORR
 
Description: Tumor response as assessed by BICR per RECIST v1.1
 
Time frame: Data are collected at baseline, then from the start of study treatment until disease progression by BICR, death, lost to follow-up, or withdrawal of consent by the subject.
 | ORR is defined as the proportion of subjects with a BOR of confirmed CR or PR. | Efficacy |
| Secondary | | | |
| To investigate the durability of U3-1402 antitumor activity in subjects with advanced or metastatic CRC | 
Title: DoR
 
Description: Tumor response as assessed by BICR per RECIST v1.1 and death date reported by Investigator
 
Time frame: Data are collected at baseline, then from the start of study treatment until disease progression by BICR, death, lost to follow-up, or withdrawal of consent by the subject.
 
Death date is collected until the subject discontinues the study.
 | DoR is defined as the time from the first documented response (CR or PR) to the date of disease progression or death due to any cause. | Efficacy |
| To further investigate the antitumor activity of U3-1402 in subjects with advanced or metastatic CRC | 
Title: ORR
 
Description: Tumor response as assessed by the Investigator per RECIST v1.1.
 
Time frame: Data are collected at baseline, then from the start of study treatment until disease progression or death, lost to follow-up, or withdrawal of consent by the subject.
 | ORR is defined as the proportion of subjects with a BOR of confirmed CR or PR. | Efficacy |
| | 
Title: DoR
 
Description: Tumor response as assessed by Investigator per
 | DoR is defined as the duration from the first documented response to | Efficacy |

| Objectives | Outcome Measures | Endpoints | Category |
|------------|--|---|----------|
| | 
RECIST v1.1 and death date reported by Investigator
 
Time frame: Data are collected at baseline, then from the start of study treatment until disease progression or death, lost to follow-up, or withdrawal of consent by the subject.
 
Death date is collected until the subject discontinues the study.
 | 
the date of disease progression or death due to any cause.
 | |
| | 
Title: DCR
 
Description: Tumor response as assessed by BICR and Investigator per RECIST v1.1.
 
Time frame: Data are collected at baseline, then from the start of study treatment until disease progression by BICR, death, lost to follow-up, or withdrawal of consent by the subject.
 | 
DCR is defined as the proportion of subjects who achieved a confirmed BOR of CR, PR, or SD.
 | Efficacy |
| | 
Title: TTR
 
Description: Tumor response as assessed by BICR and Investigator per RECIST v1.1
 
Time frame: Data are collected at baseline, then from the start of study treatment until disease progression by BICR, death, lost to follow-up, or withdrawal of consent by the subject.
 | 
TTR is defined as the time from the start of study treatment to the date of the first documentation of objective response (CR or PR) that is subsequently confirmed.
 | Efficacy |
| | 
Title: PFS
 
Description: Tumor response as assessed by BICR and Investigator per RECIST v1.1 and death date reported by Investigator.
 
Time frame: Data are collected at baseline, then from the start of study treatment until disease progression by BICR, death, lost to follow-up, or withdrawal of consent by the subject.
 
Death date is collected until the subject discontinues the study.
 | 
PFS is defined as the duration from the start of study treatment to the date of the first documentation of objective PD or death due to any cause, whichever is earlier.
 | Efficacy |

| Objectives | Outcome Measures | Endpoints | Category |
|--|---|---|---------------------|
| | 
Title: OS
 
Description: Death date as reported by Investigator
 
Time frame: Death date is collected until the subject discontinues the study.
 | OS is defined as the time from the start of study treatment to the date of death due to any cause. | Efficacy |
| To evaluate the safety and tolerability of U3-1402 in subjects with advanced or metastatic CRC | 
Title: TEAEs and other safety parameters during the study*
 
Description: Descriptive statistics of safety endpoints
 
Time frame: From the time the subject signs the main study ICF and up to 40 (+ 7) days after the last dose of study drug (ie, 5 half-lives of the ADC/the follow-up period)
 
*Although this is a secondary objective, this is a primary outcome measure.
 | Incidence of TEAEs, SAEs, AESIs (ILD and elevation of aminotransferases and TBL), ECOG PS, vital sign measurements, standard clinical laboratory parameters. AEs will be coded using the most recent version of MedDRA and will be graded using NCI-CTCAE v5.0. | Safety |
| To evaluate HER3 protein expression in tumor tissue and its relationship with efficacy | 
Title: Correlation between HER3 protein expression (as determined by HER3 IHC assay) and efficacy
 
Description: Based on a descriptive summary of the efficacy endpoints and HER3 status, a correlative analysis between HER3 protein expression level (as determined by HER3 IHC assay) and efficacy may be performed.
 
Time frame: Efficacy data are collected at baseline, then from the start of study treatment until disease progression or death, lost to follow-up, or withdrawal of consent by the subject.
 
HER3 data are collected at baseline (archival and pre-treatment tumor biopsy) and at Cycle 2.
 | HER3 protein expression in tumor tissue (as determined by IHC) and correlation with efficacy | Efficacy/ Biomarker |

| Objectives | Outcome Measures | Endpoints | Category |
|---|--|--|---------------------|
| To assess the immunogenicity incidence against U3-1402 | 
Title: Immunogenicity
 
Description: ADA prevalence, incidence, and titer for U3-1402
 
Time frame: Data are collected from the start of study treatment until the end of treatment. Additional timepoints are specified in Table 13.1.
 | 
ADA prevalence: The proportion of all subjects having a confirmed positive ADA sample at any point in time.
 
ADA incidence: The proportion of subjects having treatment-emergent ADA.
 
ADA titer will be determined for confirmed ADA-positive samples.
 
Neutralizing antibodies: When neutralizing assay becomes available confirmed ADA-positive samples may be analyzed for neutralizing activity.
 | Immuno- genicity |
| To characterize the 3 PK analytes of U3-1402 in subjects with advanced or metastatic CRC | 
Title: PK endpoints
 
Description: Serum concentration and PK parameters of U3-1402 (ADC, total anti-HER3 antibody, and MAAA-1181a)
 
Time frame: Data are collected at baseline, then from the start of study treatment until Cycle 8. Additional timepoints are specified in Table 13.1.
 | Cmax, Tmax, Ctrough, AUClast, and AUCtau | PK |
| Exploratory | | | |
| To explore changes in HER3 expression levels (mRNA in tissue and blood-based measurement) and HER3 dynamics | Not applicable | HER3 expression level (mRNA in tissue and blood-based measurement) and HER3 dynamics (mRNA and protein level) will be assessed in correlation with ORR, DoR, and PFS (confirmed by BICR). | Biomarker |

| Objectives | Outcome Measures | Endpoints | Category |
|--|------------------|---|-----------|
| To explore potential additional biomarkers that may aid in identifying subjects who will derive optimal therapeutic benefit from U3-1402 | Not applicable | Potential patient selection biomarkers (gene expression, genomic alteration, gene signatures) will be assessed in association with U3-1402 clinical activity. | Biomarker |
| To explore the impact of intrinsic and extrinsic factors of the PK of U3-1402 in subjects with advanced or metastatic CRC | Not applicable | Population PK analysis | PK |
| To evaluate the Exposure-Response for efficacy and safety endpoints | Not applicable | Exposure-Response for efficacy and safety analysis | Efficacy |

ADA = anti-drug antibody; ADC = antibody drug conjugate; AESIs = adverse events of special interest; AUClast = area under the serum concentration-time curve up to the last quantifiable time ; AUCltau = area under the serum concentration-time curve during dosing interval; BICR = blinded independent central review; BOR = best overall response; Cmax = maximum serum concentration; CR = complete response; CRC = colorectal cancer; CTCAE = Common Terminology Criteria for Adverse Events; Ctrough = trough serum concentration; DCR = disease control rate; DoR = duration of response; ECOG PS = Eastern Cooperative Oncology Group performance status; EOT = end of treatment; HER3 = human epidermal growth factor receptor 3; ICF = informed consent form; ICF = informed consent form; IHC = immunohistochemistry; ILD = interstitial lung disease; MedDRA = Medical Dictionary for Regulatory Activities; mRNA = messenger ribonucleic acid; NCI = National Cancer Institute; ORR = objective response rate; OS = overall survival; PFS = progression-free survival; PK = pharmacokinetic; PR = partial response; RECIST = Response Evaluation Criteria in Solid Tumors; SAEs = serious adverse events; SD = stable disease; TBL = total bilirubin; TEAEs = treatment-emergent adverse events; Tmax = time to reach maximum serum concentration; TTR = time to tumor response; v = version.

[figure not shown]

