3.1.2. Duration of Subject Participation

The screening period is up to 35 days. Each cycle of treatment will be 21 days. The number of treatment cycles with U3-1402 is not limited. Subjects may continue study treatment until the time of progressive disease per RECIST v1.1, unacceptable toxicity, withdrawal of consent, death, termination of the study by Sponsor or the occurrence of any of the other events specified in Section 5.7. If PD is suspected by Investigator tumor assessment, imaging must be submitted to BICR for expedited confirmation of disease progression. The decision to discontinue U3-1402 is according to Investigator judgment and should consider BICR assessment.

Tumor assessments will be performed every 6 weeks (\pm 7 days) from Cycle 1 Day 1 for the first 24 weeks then every 12 weeks (\pm 7 days) thereafter, independent of treatment cycle, until documented disease progression by BICR per RECIST Version (v) 1.1 , death, lost to follow-up, or withdrawal of consent.

There is an End-of-Treatment (EOT) Visit that takes place within 7 days after the final dose of U3-1402 or before the start of new anticancer treatment, whichever comes first. Subjects will be asked to attend a 40-Day Follow-up (F/U) Visit (+7 days) 40 days after the last U3-1402 administration. If the subject begins another anticancer therapy before the end of the 40 days (+7 days), every effort will be made to complete all of the F/U assessments prior to starting the new therapy. For further details concerning assessments performed at the EOT and F/U Visits refer to the Schedule of Events ([Table 13.1](#)).

After discontinuation from study treatment, follow-up information for determining anti-drug antibodies (ADAs) as well as survival information and subsequent anticancer therapy, if available, should be collected every 3 months (\pm 14 days). Survival F/U contact can occur via telephone contact or unscheduled visit and will continue until death, withdrawal of consent, lost

to follow-up, or study closure, whichever occurs first. Refer to [Table 13.1](#) for details. Subjects who discontinue study treatment for any reason other than documented disease progression by BICR, death, lost to follow-up, or withdrawal of consent by the subject will continue to undergo tumor assessments at the same frequency of every 6 weeks (± 7 days) from Cycle 1 Day 1 for the first 24 weeks then every 12 weeks (± 7 days) during the follow-up period.

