5.6. Prior, Concomitant and Prohibited Medications

Therapies used from the time the subject signs the ICF for study participation to the 40-Day F/U Visit (+ 7 days) after the last administration of U3-1402 will be recorded in the eCRF.

Prophylactic therapies (including any required premedications), prior therapies and all concomitant therapies will be recorded in the eCRF. Based on currently available clinical safety data for U3-1402, it is recommended that patients receive premedication with antiemetic agents. Refer to [Table 5.2](#).

All therapies received by subjects within 35 days prior to enrollment will be recorded as prior therapies. Concomitant therapies include all prescription, over-the-counter, and herbal remedies.

Therapies Requiring a Washout Period Before Enrollment

The following medications/therapies and products require a washout period before enrollment:

- Whole brain radiation therapy ≥ 14 days or stereotactic brain radiation therapy ≥ 7 days;
- Any cytotoxic chemotherapy, investigational agent or other anticancer drug(s) from a previous cancer treatment regimen or clinical study, ≥ 14 days or 5 half-lives, whichever is longer;
- Monoclonal antibodies other than immune checkpoint inhibitors, such as bevacizumab (anti-VEGF) and cetuximab (anti-EGFRs) ≥ 28 days;
- Immune checkpoint inhibitor therapy ≥ 21 days;
- Major surgery (excluding placement of vascular access) ≥ 28 days;
- Radiotherapy treatment to more than 30% of the bone marrow or with a wide field of radiation ≥ 28 days or palliative radiation therapy ≥ 14 days.

- Chloroquine or hydroxychloroquine >14 days

Prohibited Therapies/Products

The following medications/therapies and products will be prohibited during the Treatment Period through 40 days after the last dose of U3-1402:

- Other anticancer therapy, including cytotoxic chemotherapy, immune checkpoint inhibitors, or targeted agents
- Live virus vaccination (beginning from 28 days prior to Cycle 1 Day)
- Other investigational therapeutic agents
- Radiotherapy, except for palliative radiation (as long as the radiation field does not include a measurable lesion or does not interrupt treatment for more than 28 days from the planned date of administration [ie, 49 days from the last infusion date]). Radiotherapy to the thorax is also prohibited.

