5.7. Discontinuation of Study Drug

The primary reason for permanent discontinuation of U3-1402 treatment administration must be recorded. Reasons for treatment discontinuation include:

- PD per RECIST v1.1
- Clinical progression: provide date (ie, definitive clinical signs of disease progression, but a recent radiographic assessment did not meet the criteria for PD according to RECIST v1.1)
- AE (See Section 5.4)
- Death
- Pregnancy
- Withdrawal by subject (**to discontinue study drug**). NOTE: In this section, this is only withdrawal for treatment with study drug and is NOT the same thing as a complete withdrawal from the study. Discuss with the subject that they will remain in the study (ie, continue with study visits and assessments, including survival follow-up).
 - Lost to follow-up
 - Protocol violation (specify)
 - Study terminated by Sponsor
 - Other, specify (eg, Investigator discretion)

If there is evidence that the subject is receiving benefit from treatment even though the subject has met a criterion for discontinuation as listed above, the subject may remain on study treatment after discussion with and approval from the Sponsor.

Discontinued subjects will be followed for survival, either through direct contacts or by collecting public records (eg, death certificates) as allowed by local laws.

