7. EFFICACY ASSESSMENTS

7.1. Tumor Assessments for Efficacy

Clinical activity of U3-1402 will be assessed by evaluating tumor response.

Tumor assessments will be conducted as indicated in the Schedule of Events ([Table 13.1](#)). At screening, perform radiographic tumor assessments (CT/MRI) of the chest, abdomen, pelvis, brain, and all sites of disease. Investigator determined tumor radiologic assessments of the brain (if stable brain metastasis was present at baseline), chest, abdomen, and pelvis and other relevant anatomic locations where imaging was performed at screening or newly suspected disease should be performed every 6 weeks (\pm 7 days) from Cycle 1 Day 1 for the first 24 weeks then every 12 weeks (\pm 7 days) thereafter, independent of treatment cycle, and will continue to be performed until documented disease progression by BICR per RECIST v1.1 ([Section 13.4](#)), death, lost to follow-up, or withdrawal of consent (withdrawal by subject from the study as indicated on the end of study form: NOTE: This indicates that the subject withdraws consent and refuses to undergo any further study procedures or be followed for long-term survival). Subjects who discontinue study treatment for any reason other than documented disease progression by BICR, death, lost to follow-up, or withdrawal of consent by the subject will continue to undergo tumor assessments at the same frequency of every 6 weeks (\pm 7 days) from Cycle 1 Day 1 for the first 24 weeks then every 12 weeks (\pm 7 days) during the Follow-up period.

The same methodology (CT or MRI) and scan acquisition techniques (including use or nonuse of IV contrast unless medically infeasible, ie, newly developed AE or allergy to contrast agent) as were used for the screening assessments should be used throughout the study for all assessments for each subject unless prior approval is obtained from the Sponsor. Unscheduled tumor assessments may be conducted if progression is suspected. Tumor assessments should not be delayed by dose interruptions; they are timed relative to Cycle 1 Day 1. Tumor assessments should be performed per RECIST v1.1 ([Section 13.4](#)).

Objective responses must be confirmed at least 4 weeks later (eg, generally at the next tumor assessment time point). Also, perform CT or MRI of the brain within a target of 1 week after a subject achieves a complete response (CR).

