11.5. Statistical Analyses

11.5.1. Efficacy Analyses

11.5.1.1. Primary Efficacy Analyses

The primary efficacy endpoint is ORR (the proportion of subjects with a best overall response [BOR] of CR or PR) as assessed by BICR per RECIST v1.1. CR/PR will be confirmed with a follow-up tumor assessment at least 4 weeks apart.

ORR will be summarized with the 2-sided 95% CI using the Clopper-Pearson method in the FAS. For the computation of ORR, subjects with BOR of “not evaluable (NE)” will be included in the FAS and will be considered non-responders. Data will be summarized by cohort if applicable. No formal comparison between the 2 cohorts is planned.

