13.4.2.4.3. Best Overall Response: All Time Points

Best response determination in trials where confirmation of complete or partial response is required: when SD is believed to be best response, it must also meet the protocol-specified minimum time from baseline, 6 weeks (-1 week). If the minimum time is not met when SD is otherwise the best time point response, the subject's best response depends on the subsequent assessments. Complete or partial responses may be claimed only if the criteria for each are met at a subsequent time point as specified in the protocol. In this circumstance, the best overall response can be interpreted as in [Table 13.3](#).

Table 13.3: Best Overall Response when Confirmation of CR and PR Required

| Overall Response – First Time Point | Overall Response – Subsequent Time Point | BEST Overall Response |
|-------------------------------------|--|--|
| CR | CR | CR |
| CR | PR | SD, PD or PR ^a |
| CR | SD | SD provided minimum criteria for SD duration met, PD |
| CR | PD | SD provided minimum criteria for SD duration met, PD |
| CR | NE | SD provided minimum criteria for SD duration met, NE |
| PR | CR | PR |
| PR | PR | PR |
| PR | SD | SD |
| PR | PD | SD provided minimum criteria for SD duration met, PD |
| PR | NE | SD provided minimum criteria for SD duration met, NE |
| NE | NE | NE |

CR = complete response; PR = partial response; SD = stable disease; PD = progressive disease; NE = not evaluable.

^a If a CR is truly met at first time point, then any disease seen at a subsequent time point, even disease meeting PR criteria relative to baseline, makes the disease PD at that point (since disease must have reappeared after CR). Best response would depend on whether minimum duration for SD (6 weeks) was met. However, sometimes ‘CR’ may be claimed when subsequent scans suggest small lesions were likely still present and in fact the subject had PR, not CR at the first time point. Under these circumstances, the original CR should be changed to PR and the best response is PR.

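### Could responses reached on a later anticancer drug be counted in the primary response rate because scanning continues after new therapy starts?

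*Combined protocol and SAP*

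**What the plan says.** Table 2.1 (and the synopsis) sets the collection window for primary ORR: "Data are collected at baseline, then from the start of study treatment until disease progression by BICR, death, lost to follow-up, or withdrawal". The last item refers to consent. Section 7.1 keeps some subjects on the scan schedule, at the same frequency, after treatment ends. It describes them thus: "Subjects who discontinue study treatment for any reason other than documented disease progression by BICR, death, lost to follow-up, or withdrawal of consent". Section 5.7 allows treatment to stop without RECIST progression, for an adverse event or for clinical progression, described as "definitive clinical signs of disease progression, but a recent radiographic assessment did not meet the criteria for PD according to RECIST v1.1".

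Section 11.5.1.1 states: "The primary efficacy endpoint is ORR (the proportion of subjects with a best overall response [BOR] of CR or PR) as assessed by BICR". It adds a confirmation interval and the handling of subjects who are not evaluable, but nothing on new therapy. Section 11.6 (interim counts) and Section 13.4.2.4.3, headed "Best Overall Response: All Time Points", are also silent on it.

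On later treatment, Section 5.6 says of a list that includes other anticancer therapy: "The following medications/therapies and products will be prohibited during the Treatment Period through 40 days after the last dose of U3-1402". Section 3.1.2 says that "survival information and subsequent anticancer therapy, if available, should be collected every 3 months".

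Sections 11.1 and 11.7 announce a separate SAP, to be final before database lock, that will hold the efficacy definitions. Section 11.2 plans no statistical test.

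**The concern.** In a single-arm trial ORR is read against a fixed reference, here 5% historical and 20% clinically meaningful. Extra scans can only add confirmed responses, so counting scans taken on a later drug can only push ORR up, and there is no control arm to offset it.

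The route is real. A subject stops U3-1402 for toxicity or clinical decline without BICR progression, starts another drug, stays on the scan schedule, and reaches or confirms a partial response there. Disease control rate, time to response and best percent change in tumor size would be exposed in the same way. Section 11.5.1.2 explicitly defers censoring of DoR, PFS and OS to the SAP but does not name ORR, which makes the silence look like an oversight.

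The count matters near the benchmark in Table 11.2. One responder decides whether the exact lower limit lies above 5%.

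**Working it through.** **1. The plan's own figures.** Exact binomial tails and Clopper-Pearson limits reproduce Table 11.2:

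- 8/68: P(X ≥ 8) = 97.4% at a true ORR of 20% and 2.0% at 5%; 95% CI 5.2% to 21.9%.
- 9/80: P(X ≥ 9) = 98.7% and 1.8%; 95% CI 5.3% to 20.3%.
- One responder fewer gives lower limits of 4.2% (7/68) and 4.4% (8/80).

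**2. Inputs for a literal reading in which every scan counts.**

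- Response rate on the next drug, r: 1% and 1.6%, the later-line rates in Section 1.1.1.
- Switchers before BICR progression, m: not given in the documents. Assumed range 5 to 20 of 68.
- A guide to m from Section 1.1.5, counting stops for clinical progression or an adverse event: breast study (6 + 10)/94 = 17.0%, and 0.170 × 68 = 11.6; lung study (2 + 2)/24 = 16.7%, and 0.167 × 68 = 11.3. So m = 12 is a central case if every subject discontinues and all of these switch.

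**3. Expected borrowed responders, m × r.**

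- 5 × 0.01 = 0.05
- 12 × 0.01 = 0.12; 12 × 0.016 = 0.19
- 20 × 0.016 = 0.32

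As ORR: 0.05/68 = 0.07 points and 0.32/68 = 0.47 points, or 0.1 to 0.5 rounded. The chance of at least one, 1 − (1 − r)^m, is 4.9% (m = 5, r = 1%), 11.4% to 17.6% (m = 12) and 27.6% (m = 20, r = 1.6%).

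**4. Effect at the benchmark.** Let p be the true ORR. Switchers respond with probability 1 − (1 − p)(1 − r) and the others with p. Convolving the two binomials gives P(X ≥ 8 of 68):

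| True ORR | No borrowing | m = 5 | m = 12 | m = 20 |
|---|---|---|---|---|
| 5% | 2.0% | 2.2% | 2.4–2.6% | 2.7–3.1% |
| 10% | 37.0% | 37.7–38.1% | 38.7–39.7% | 39.8–41.5% |
| 20% | 97.4% | 97.5% | 97.6–97.7% | 97.7–97.8% |

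Ranges run from r = 1% to r = 1.6%. For 9/80 at a true ORR of 5%, the 1.8% becomes 2.0% (m = 5, r = 1%) to 2.8% (m = 20, r = 1.6%).

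**5. Wider assumptions.** With 5% of 68 switching and r = 1%: 68 × 0.05 × 0.01 = 0.03. With 26.6% of 80 switching (the breast study's share when withdrawals and other reasons are added, 25/94) and r = 5%: 80 × 0.266 × 0.05 = 1.06.

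**6. What already limits the route.** Suspected progression goes to expedited BICR. The ban on other anticancer therapy runs 40 days past the last dose, so with 6-weekly scans in the first 24 weeks another scan usually falls near or before the permitted start; scans are 12-weekly after that. Partial response is measured against the baseline before U3-1402 and needs confirmation at least 4 weeks later. At the interim, after about two assessments per subject, there is little time for a switch, a response and its confirmation.

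**The case for a change.** The strongest argument for a written rule is that it costs one sentence and is best fixed before open-label data are read, since choosing it afterwards could look driven by the results. The step from 7/68 to 8/68 shows that a single response can matter. The central range may also be too low. The count of 12 leaves out withdrawals, other reasons and investigator-called progression that BICR does not confirm, and the model omits a partial response on U3-1402 that is confirmed only after the switch. At r = 5%, the protocol's historical reference, 20 switchers would raise P(X ≥ 8 of 68) at a true ORR of 5% from 2.0% to 6.7%. The 40-day ban is not absolute, because Section 3.1.2 foresees an earlier start.

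These points stand as limits on precision, so the figures above are not an upper bound. But r = 5% is well above the 1% and 1.6% that the protocol reports for later-line drugs, and even those rates are not measured from a baseline with an earlier drug in between, so they may overstate borrowing.

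A cut at new therapy has a bias of its own. A genuine U3-1402 response not yet confirmed at the switch would become a non-response. At a true ORR of 20%, 0.20 × 68 = 13.6 responders are expected; losing 0.32/13.6 = 2.4% of them offsets the largest figure in the central range. Which set of scans is primary and which is sensitivity is therefore partly a matter of choice.

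It could also be said that a cut cannot be programmed because later therapy is collected only where available (Section 3.1.2). That does not hold. Section 5.6 has therapies recorded in the eCRF up to the 40-day visit, Section 6.6 reviews new anticancer treatment at each 3-monthly follow-up, and Table 13.1 has its own row for it.

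**Conclusion.** No change to the plan is called for. The protocol text is silent on whether scans after new anticancer therapy count toward primary response, but the time frame in Table 2.1 is a collection window and no passage tells the analyst to count every scan collected. Choosing the scans that enter best overall response is an efficacy definition, which Section 11.7 assigns to the SAP. Naming DoR, PFS and OS censoring separately does not exclude ORR, because a proportion is not censored. Continued scanning is sensible in itself, and the data needed for either choice are planned.

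If every scan did count, the bias would be upward and small: 0.05 to 0.32 expected responders of 68, or 0.1 to 0.5 points of ORR, assuming 5 to 20 switchers and response rates of 1% to 1.6%. The wider range of 0.03 to 1.06 needs switching shares of 5% to 26.6% among 68 to 80 subjects and rates of 1% to 5%. The number of switchers is an assumption throughout. With no test planned and an estimate reported with its exact interval, a shift within the central range leaves the trial's conclusion sound. This is a detail that analysts settle sensibly in the SAP.
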